9.4 Statistical Analyses

9.4.1 General Approach

Prior to analysis, all primary and secondary outcome measures will be summarized with descriptive statistics (mean \pm standard deviation (SD) or median and IQR), their distributions examined, tested for normality and transformed using log base 10 as needed. Additionally, all

demographics will be summarized using mean \pm SD or median and IQR, for continuous variables and frequencies and percentages for categorical variables. Results from statistical testing for continuous variables, will be presented with p-values and 95% confidence intervals for tests using means or medians and IQR if a non-parametric test is used. For categorical variables, the chi-square or Fisher's exact test will be performed to examine whether treatment arms differ with regard to demographics and other baseline variables. Similarly, for side effects, descriptive statistics and Fisher's exact tests will be performed for possible differences between the treatment arms. Regardless of type statistical test, all will be two-sided.

The primary efficacy endpoint is change in pain level as measured on the NRS at baseline (pre intervention) and at post intervention (either 1-hour post-enrollment or at time of ED discharge, whichever occurs first) in both treatment arms. The NRS is an ordinal variable, measured on a 0-10 scale and will be treated as a repeated measure. To determine differences in pain level between GNB and conventional analgesia treatment arms, a 2-factor analysis of variance in repeated measures will be performed where treatment arm is the grouping factor and time (pre/post) is the repeated measure. To adjust for multiple comparisons, post-hoc pairwise Tukey-Kramer tests will be performed. Results will be presented as means \pm 95% confidence intervals for each treatment arm/time point. Shapiro-Wilkes test will be used to test for normality. If not normally distributed, data will be transformed using log base 10 transformation. If missing time points, analysis type will change to a mixed general linear model where treatment arm is a fixed factor and time is random.

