Those patients who satisfy all inclusion criteria will be offered enrollment and consented by a participating emergency physician or RA. Upon consenting, patients will be asked to rate their knee pain on the NRS. This initial evaluation is based on the current severity of the pain, regardless of whether patients received any analgesics prior to obtaining radiography. Study will not begin until plain film imaging has been reviewed by a radiologist, at which point patients will be considered for eligibility.

Utilizing a random number generator, patients will be randomized to either the intervention arm (GNB) or the control (conventional analgesia) arm. Within the intervention arm, a three-point GNB will be performed under ultrasound guidance using 80% of ideal body weight (80% of *actual* body weight if BMI is less than 25 kg/m^2) dosing of 0.5% bupivacaine with 4 mg dexamethasone, divided into three separate aliquots (5 mL of 0.5% bupivacaine with 1-2 mg dexamethasone) which will be administered to the SMGN, SLGN, and IMGN. The performing

physician will first identify all landmarks via ultrasound, which include the superomedial and -lateral knee (aligning the probe longitudinally with the femoral condyle) and the inferomedial knee (aligning the probe longitudinally with the tibial condyle). Color doppler will be applied to note any vascular structures within the field of view of injection. The patient will be placed on the cardiopulmonary monitor prior to the GNB. The GNB will be performed via ultrasound guidance in real-time.

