9 STATISTICAL CONSIDERATIONS

9.1 Statistical Hypotheses

Primary endpoints:

- H_0 : Mean change in pain levels pre / post GNB = Mean change in pain levels pre / post conventional therapy
- H_1 : Mean change in pain levels pre / post GNB \neq Mean change in pain levels pre / post conventional therapy

Secondary endpoints:

- H_0 : Mean duration of analgesia for patients receiving GNB = Mean duration of analgesia for patients receiving conventional therapy
- H_1 : Mean duration of analgesia for patients receiving GNB \neq Mean duration of analgesia for patients receiving conventional therapy
- H_0 : Mean APS-POQ-RED score for patients receiving GNB = Mean APS-POQ-RED score for patients receiving conventional therapy
- H_1 : Mean APS-POQ-RED score for patients receiving GNB \neq Mean APS-POQ-RED score for patients receiving conventional therapy
- H_0 : Mean ED LOS for patients receiving GNB = Mean patient satisfaction for patients receiving conventional therapy
- H_1 : Mean ED LOS for patients receiving GNB \neq Mean patient satisfaction for patients receiving conventional therapy

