9.2 Sample Size Determination

To determine the number of patients needed in each study arm for sufficient sample size we considered the primary outcome of change in pain levels pre/post treatment as measured by the NRS as this was the largest sample size needed to detect a clinically meaningful effect.

The sample size was loosely based on an RCT by [Shanahan et al. 2023](#), for which the mean change in the visual analog scale (VAS: 0-10 scale) from baseline at 2 weeks was 3.5 (GNB) and 0.7 (sham injection group). Assuming the mean change in NRS pain score pre/post treatment between the GNB and standard analgesia (difference in difference) will be smaller in a shorter period of time, group sample size of 17 (each group) will achieve 80% power to detect a difference in NRS between treatment arms as small as 1.6, with alpha set at 0.05 and standard deviation of differences set at 2.0 using a two-sided two-sample equal-variance t-test with a 5-10% loss to follow-up at the 24 hour mark.

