9.4.4 Baseline Descriptive Statistics

All demographics will be summarized using mean \pm SD, for continuous variables and frequencies and percentages for categorical variables. Standard statistical tests (chi-square and 2-sample t-tests or Wilcoxon rank-sum test) will be performed to examine whether patients differ with regard to demographics and other baseline variables in the 2 study arms.

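### The primary pre/post ANOVA is valid but amounts to a change-score t-test that fixes the slope on baseline NRS at 1; baseline adjustment would cost almost nothing, with a gain the protocol does not allow to be fixed

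*Protocol*

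**What the plan says.** Section 9.1 states the primary null hypothesis as equality of mean change: "Mean change in pain levels pre / post GNB = Mean change in pain levels pre / post conventional therapy". Section 9.2 sizes the trial on that change, with "standard deviation of differences set at 2.0 using a two-sided two-sample equal-variance t-test", a difference of 1.6 and 17 patients per arm. Section 9.4.1 describes the endpoint in the same way ("The primary efficacy endpoint is change in pain level as measured on the NRS at baseline (pre intervention) and at post intervention") and names the model: "a 2-factor analysis of variance in repeated measures will be performed where treatment arm is the grouping factor", with pre/post time as the within-patient factor. If time points are missing, the "analysis type will change to a mixed general linear model where treatment arm is a fixed factor and time is random".

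Section 8.1 has the NRS taken before randomization, so a proper baseline covariate exists for every patient. Neither the main model nor the fallback uses it as one. Baseline is otherwise only compared between arms: section 9.4.4 says that standard tests "will be performed to examine whether patients differ with regard to demographics and other baseline variables in the 2 study arms", and no action follows from the result.

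**The concern.** Analysing change means subtracting each patient's baseline in full, as if a patient who starts one point higher would also end one point higher. If the true slope of post-score on baseline is smaller than that, subtraction over-corrects. The arm that happens to start with more pain then appears to improve more, whatever the treatment did.

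Analysis of covariance estimates the slope from the data instead of fixing it. It targets the same between-arm difference and takes the chance baseline difference out of the estimate. In a trial of 34 patients such differences are not negligible, and a significance test of baseline does nothing to correct them. At stake is precision, and how far the estimate depends on the baseline draw. Type I error is not at stake.

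**Working it through.** **Inputs from the protocol.** Difference 1.6, SD of change 2.0, two-sided alpha 0.05, 17 per arm, stated power 80% (section 9.2); entry NRS 5 to 10 (section 5.1).

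**Inputs not in the protocol, taken as ranges.** Baseline SD 1.0, 1.25 and 1.5; pre/post correlation r from 0.2 to 0.6. The SD of change is held at 2.0 throughout.

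**1. The plan's own figure.** Standard error of the difference in mean change = 2.0 × sqrt(2/17) = 0.686. Noncentral t, 32 df, noncentrality 1.6/0.686 = 2.33: power 0.62, not 0.80. The stated inputs need 26 per arm for 80%. That is a separate problem; 0.62 serves here only as the reference.

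**2. Equivalence.** With two arms and two times, the arm-by-time F equals the square of the t statistic on change. On one simulated data set of 17 per arm, both came to 14.004. Section 9.4.1 does not name the arm-by-time term, but the hypothesis in section 9.1 is that contrast.

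**3. Effect of a chance baseline difference.** Shift in the change-score estimate per point of baseline difference = -(1 - slope).
- SD of the baseline mean difference = baseline SD × sqrt(2/17): 0.34 at SD 1.0, 0.51 at SD 1.5.
- At slope 0.4 and SD 1.5, a one-SD difference shifts the estimate by 0.6 × 0.51 = 0.31 points, about 19% of the 1.6 target.
- A full 1-point difference would shift it by 0.6 points, but is about a 1.9-SD event (1/0.51).

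This is not error on top of the 0.686 standard error. It is a component of it that adjustment removes.

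**4. Power with baseline as covariate.**
- Post SD = r × SDpre + sqrt(r² × SDpre² - SDpre² + 4), which keeps the SD of change at 2.0.
- Slope = r × SDpost / SDpre.
- Residual SD = SDpost × sqrt(1 - r²).
- Standard error = residual SD × sqrt((2/17) × (1 + 1/30)), with 31 df; the 1/30 allows for estimating the slope.

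Example, SDpre 1.5 and r 0.3: SDpost = 0.45 + sqrt(0.2025 - 2.25 + 4) = 1.85; slope 0.37; residual SD 1.76; standard error 0.614; power 0.71.

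| r | SDpre 1.0: slope, power | SDpre 1.25: slope, power | SDpre 1.5: slope, power |
|---|---|---|---|
| 0.2 | 0.39, 0.65 | 0.29, 0.70 | 0.22, 0.78 |
| 0.3 | 0.62, 0.62 | 0.48, 0.65 | 0.37, 0.71 |
| 0.4 | 0.87, 0.61 | 0.69, 0.62 | 0.55, 0.66 |
| 0.5 | 1.15, 0.61 | 0.92, 0.60 | 0.76, 0.62 |
| 0.6 | 1.46, 0.63 | 1.19, 0.61 | 1.00, 0.60 |

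The reference in every cell is 0.62. The worst case is a slope of exactly 1: the residual SD stays at 2.0, the standard error is 0.697 and power is 0.604, a loss of 0.619 - 0.604 = 0.015.

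**The case against.** The strongest reply is that nothing here is inconsistent. Hypothesis, sample size and analysis all concern mean change; the test is valid; and baseline is not ignored, since it is one level of the repeated measure. All of that stands. A reader might infer that the primary test is biased or that its error rate is wrong. The documents do not support either: over randomization the change-score estimate is unbiased, and the loss is in precision and in dependence on the observed baseline difference.

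A reader might also infer that a slope below 1 is guaranteed, because entry requires NRS 5 to 10 and because of the baseline score section 4.1 says "This initial evaluation is based on the current severity of the pain, regardless of whether patients received any analgesics prior to obtaining radiography". That does not follow. Under a linear relation, selecting on baseline lowers the correlation but not the slope, and regression to the mean acts on both randomized arms and cancels between them. Possible earlier analgesia fixes no slope either.

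Larger gains are available on paper by assuming equal pre and post SDs. At correlation 0.5 that needs a baseline SD of 2.0 (from 2.0 / sqrt(2 × 0.5)), whereas a uniform spread over the integers 5 to 10 has an SD of only 1.71. I have not relied on that case.

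Finally, it may be said that covariates belong in an analysis plan not seen here. But the protocol itself names the primary model and its fallback, so this choice has been made, not left open.

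**Conclusion.** The point holds as a low-cost improvement to a valid analysis. The size of the gain is unknown, because the protocol gives no correlation and no separate SDs. Under the assumed ranges, the change in power runs from about -1.5 to +16 points. For baseline SD 1.0 to 1.25 it is only about -1.5 to +8. The gain disappears as the slope approaches 1.

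The case for changing rests on the asymmetry: the possible loss is trivial, the data are already collected, and adjustment takes the chance baseline difference out of the estimate. A reader might hope that adjustment restores the 80% power claimed in section 9.2. In none of the cases tabulated does it reach 80%, so the sample size needs its own correction.

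**What to change.** In section 9.4.1, make the primary analysis a linear model of post-intervention NRS on treatment arm and baseline NRS. Report the adjusted between-arm difference with its 95% confidence interval and p-value. Keep the unadjusted difference in change as a sensitivity analysis, and reword the missing-data fallback so that it targets the same adjusted contrast.

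The cost is protocol wording, one degree of freedom and at most about 1.5 points of power. No new data are needed. The mismatch in section 9.2 between 17 per arm and 80% power must be dealt with separately.

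### Section 9.4.1 does not say which effect of the repeated-measures ANOVA decides the primary endpoint, and the follow-up tests, display and missing-data model it names do not target the difference in mean change

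*Protocol*

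**What the plan says.** Section 9.1 states a single primary null hypothesis: "Mean change in pain levels pre / post GNB = Mean change in pain levels pre / post conventional therapy". Section 9.2 calls the same quantity a difference in difference. It claims that 17 per group "will achieve 80% power to detect a difference in NRS between treatment arms as small as 1.6", with "standard deviation of differences set at 2.0" and alpha 0.05, "using a two-sided two-sample equal-variance t-test".

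Section 9.4.1 then sets out the primary analysis:

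- A two-factor repeated-measures ANOVA, with arm as the grouping factor and pre/post time as the repeated factor, is given the task of finding differences between arms. No effect of that model is named as decisive.
- "To adjust for multiple comparisons, post-hoc pairwise Tukey-Kramer tests will be performed".
- Primary results are to be shown as means with "95% confidence intervals for each treatment arm/time point".
- If time points are missing, the analysis becomes a mixed model with arm as a fixed factor and time as a random one. No arm-by-time term is mentioned.

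Earlier in the same section, a general sentence promises p-values and 95% confidence intervals for tests based on means.

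**The concern.** A two-by-two repeated-measures ANOVA yields an arm main effect, a time main effect and an arm-by-time interaction. Only the interaction corresponds to 9.1. The text does not say so, and each specific instruction after the ANOVA sentence points elsewhere: to comparisons of pairs of cell means, to intervals for single cell means, and to a fallback whose only named fixed effect is arm.

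An analyst could therefore report the interaction, the arm main effect or a Tukey-adjusted comparison of post-treatment means, and claim to have followed the protocol. These tests differ in power, and the arm main effect also estimates a different quantity. The trial is open-label (6.3) and looks at the primary endpoint after 30 patients (9.4.5), so a choice left open could be made with results in view.

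**Working it through.** **Inputs.** From 9.2: 17 per arm, difference in change 1.6, SD of change 2.0, two-sided alpha 0.05. The protocol gives no baseline SD and no pre/post correlation. I assume baseline SD 1.2 to 1.5 and correlation 0.2 to 0.5.

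**1. The plan's own figure.** By the normal approximation, n = 2 × (1.960 + 0.842)² × 2.0² / 1.6² = 24.5, so 25 per arm; the exact t calculation gives 25.5, so 26. At 17 per arm the noncentrality is 1.6 / (2.0 × √(2/17)) = 2.33 against a critical t of 2.04 on 32 df, and power is 62%. The stated 80% is not reproduced. A difference of 2.0 with SD 2.0 does give 16.7, so 17. This is a separate matter; 62% is the benchmark below.

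**2. The ANOVA contains the right test.** Let D be the difference between arms in mean change, s the pooled SD of change, and n the number per arm.

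- Interaction sum of squares = nD²/4, on 1 df.
- Within-patient error mean square = s²/2, on 2(n − 1) = 32 df.
- F = (nD²/4) / (s²/2) = nD² / (2s²) = [D / (s√(2/n))]² = t².

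A numerical check on simulated data gave 0.002925 for both F and t².

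**3. The pairwise tests do not contain it.** Four cell means give six pairs: pre versus pre, post versus post, pre versus post within each arm, and two cross pairs. The difference in change is (GNB post − GNB pre) − (control post − control pre). It uses all four means and is none of the six. Intervals for single cell means do not provide an interval for it either.

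**4. Cost of taking another effect as primary.** With baseline SD s₁ and correlation r, a change SD of 2.0 fixes the post-treatment SD: s₂ = r·s₁ + √(4 − s₁²(1 − r²)).

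- *Arm main effect.* It averages pre and post, so the expected difference is 1.6/2 = 0.8, with SD √(s₁² + s₂² + 2r·s₁s₂)/2. For s₁ = 1.2 and r = 0.2, s₂ = 1.86, the SD is 1.20, the standardised difference is 0.8/1.20 = 0.67, and power is 47%.
- *Tukey post versus post.* The critical value is 3.832/√2 = 2.71 (four means, 32 df) in place of 2.04. Power is from 40,000 simulated trials per row, once with error pooled over the four cells and once with the post-treatment SD only.

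| s₁ | r | s₂ | Interaction | Arm main effect | Tukey, pooled error | Tukey, post SD only |
|---|---|---|---|---|---|---|
| 1.2 | 0.2 | 1.86 | 62% | 47% | 59% | 43% |
| 1.2 | 0.5 | 2.31 | 62% | 31% | 45% | 26% |
| 1.5 | 0.2 | 1.66 | 62% | 46% | 60% | 55% |
| 1.5 | 0.5 | 2.27 | 62% | 28% | 41% | 27% |

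**5. The tests answer different questions.** As an illustration, give both arms the same change but set the true baselines 1 point apart (equal SDs, correlation 0.3 to 0.7, 20,000 trials each). The interaction rejects in 5% of trials, the arm main effect in 22% to 54%, and Tukey post versus post in 8% to 19%. Randomisation makes the baselines equal in expectation, so these are not error rates to expect in this trial. They show only that the latter two do not test the hypothesis in 9.1.

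**The case against.** A reader might infer that the primary decision rests on the Tukey-Kramer tests. The text does not support that. It assigns the between-arm question to the ANOVA and labels the pairwise tests post-hoc; the stricter threshold of 2.71 would apply to the primary question only if Tukey replaced the ANOVA test. A reader might also infer that no interval for the effect will be reported, or that the efficacy claim will be built on within-arm pre/post tests. The general sentence on p-values and confidence intervals weakens the first inference, and no section states the second.

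It can further be said that 9.1 already fixes the quantity, that a standard two-factor ANOVA includes the interaction, and that the model term could be left to an analysis plan not shown here. Under randomisation, a post-only comparison also has the same expected value as the difference in change, and with pooled error and low correlation it loses only a few points of power (59% to 60% against 62%).

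Much of this stands, and it limits the point to an unnamed decisive effect. It does not remove the point. The protocol is not merely silent: it prescribes follow-up tests and a display that miss its own hypothesis, and the general sentence names no contrast. The defence is weakest for the fallback model, where the interaction cannot be read in from convention because the only fixed effect named is arm.

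**Conclusion.** The concern holds in this limited form. The planned ANOVA contains exactly the test that 9.1 and 9.2 require, but 9.4.1 does not name it, and its named follow-up, display and missing-data model neither test nor estimate the difference in mean change.

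Under the 9.2 inputs, the interaction has 62% power. The arm main effect has about 28% to 47%. Tukey post versus post has about 26% to 60%, or 41% to 60% with the pooled error of a conventional repeated-measures ANOVA; the low end needs separate variances, which the protocol does not mention. All figures except the 62% depend on the assumed baseline SD and correlation.

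Naming the right test does not restore 80% power. That shortfall belongs to the sample-size calculation in 9.2.

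**What to change.** In 9.4.1:

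- Name one primary test, two-sided at 0.05: the between-arm difference in change. This can be the arm-by-time contrast or, preferably, the arm term in a model for post-treatment NRS adjusted for baseline NRS. The adjusted model's residual SD, s₂√(1 − r²), is never above the SD of change: 2.31 × 0.866 = 2.00 at s₁ = 1.2, r = 0.5, and 1.66 × 0.980 = 1.62 at s₁ = 1.5, r = 0.2.
- Report that contrast as a point difference with its 95% CI.
- Use the same contrast in the missing-data model, with time as a fixed factor and the arm-by-time term included.
- Present the four cell means descriptively.
- Drop Tukey-Kramer for the primary endpoint, or label it supportive only.

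The cost is a few sentences. The data are already collected under the plan, and no further patients are needed for this change.

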2.3.2 Known Potential Benefits

Patients with knee OA can often have flares of severe pain, requiring ED visits for pain control. Several case reports and small case series have demonstrated the efficacy and safety of the genicular block performed in the emergency department for managing acute or chronic pain associated with knee osteoarthritis ([Bhattaram 2024](#), [Kong 2023](#), [Sobel 2021](#)). Moreover, a recent randomized controlled trial published in the rheumatology literature on ambulatory

patients demonstrated the that the genicular nerve block provides longer term pain relief in patients with knee osteoarthritis ([Shanahan 2022](#)). In this study, patients treated with a one-time three-point ultrasound-guided GNB reported improvements in pain scores and decreased disability as measured on the Western Ontario and McMasters Universities Osteoarthritis Index (WOMAC) and the Intermittent and Constant Osteoarthritis Pain scale compared to the control group who received a sham injection for up to 12-weeks after the block ([Shanahan 2022](#)). Immediate potential benefits include improved or relief of knee pain, improved mobility and ability to ambulate, reduced need for alternative analgesics (including opioids), reduced need for admission for pain control and need for inpatient physical therapy evaluation and treatment, quicker disposition from the emergency department due to quick and effective pain control. Moreover, in our anecdotal experience, patients whom we have treated with a GNB have reported high levels of satisfaction with the procedure and have reported complete pain relief for greater than 24-hours after the block. Even when symptoms began to return, patients reported that they were not as severe as those which initially promoted them to visit the ED. Moreover, to our knowledge, none of the patients on whom we have performed the GNB have returned to the ED for recurrent pain. Therefore, the GNB might also provide the appropriate bridge from ED care to outpatient follow-up, thereby reducing the need for patients to return to the ED for recurrent pain.

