5 STUDY POPULATION

5.1 Inclusion Criteria

To be eligible to participate in this study, an individual must meet all the following criteria:

1. Patient presenting to ED with atraumatic knee pain
2. Provision of signed and dated informed consent form and stated willingness to comply with all study procedures and availability for the duration of the study
3. Equal to or over the age of 18 years
4. Have plain film radiography of the knee obtained during the encounter
5. Pain measured on NRS between 5 and 10

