9.4.2 Analysis of the Secondary Endpoint(s)

Two secondary endpoints to be measured are length of time until additional analgesia needed after initial treatment (GNB or conventional analgesia) and ED LOS. Both of these endpoints are interval/ratio variables measured in hours. Additional analgesia time will be assessed at 24-36 hours after intervention by phone call or EMR if still in the ED or admitted to the hospital. ED-LOS will be assessed by EMR chart review. To assess differences between treatment arms for both these time endpoints, either a 2-sample t-test (normally distributed) or a Wilcoxon rank-sum test (positively skewed) will be performed.

The final secondary endpoint is the 6 questions on the modified APS-POQ-RED administered. Each of 5 questions are on an ordinal scale from 0-10. For each question, a 2-sample t-test will be performed.

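### The non-normality fallback for the primary endpoint takes log10 of a 0-10 pain score, which is undefined for complete relief; the missing-data model also needs rewording

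*Protocol*

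**What the plan says.** Protocol section 9.4.1 describes the outcome thus: "The NRS is an ordinal variable, measured on a 0-10 scale and will be treated as a repeated measure". The default primary analysis is a two-factor repeated-measures ANOVA, with arm as the grouping factor and pre/post as the repeated factor. Results are to be shown as means with "95% confidence intervals for each treatment arm/time point".

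Two conditional rules follow:

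- **Non-normality, judged by Shapiro-Wilk:** "If not normally distributed, data will be transformed using log base 10 transformation". No offset or handling of zeros is given. The opening of 9.4.1 applies the same log10 remedy to all primary and secondary outcomes where needed.
- **Missing time points:** the "analysis type will change to a mixed general linear model where treatment arm is a fixed factor and time is random".

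Related statements elsewhere:

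- Section 5.1 sets the entry range: "Pain measured on NRS between 5 and 10".
- Section 9.1 states the primary null hypothesis as equal mean pre/post change in the two arms.
- Section 9.2 sizes the trial on a 1.6-point difference in that change, with SD 2.0 and 17 per arm.
- Section 9.4.1 mentions "medians and IQR if a non-parametric test is used" when describing how continuous results are presented.
- Section 9.4.2 says that for the two time endpoints, if skewed, "a Wilcoxon rank-sum test (positively skewed) will be performed".

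**The concern.** The first rule cannot be carried out on data the trial can be expected to produce. Zero is a legitimate score and means complete relief. Section 2.3.2 says, from the investigators' anecdotal experience, that patients given the block "have reported complete pain relief for greater than 24-hours after the block". Because nobody enters below 5, every zero is a post-treatment score, and zeros will be more frequent in whichever arm gets better relief. An analyst who follows the text must either exclude those patients or choose an offset the protocol does not give, in an open-label trial with 17 patients per arm.

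Even where it is defined, the log scale answers a different question from the one in section 9.1.

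The second rule has a lesser fault. It calls the two designed occasions random and names neither an arm-by-time term, which carries the section 9.1 hypothesis, nor a patient effect.

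**Working it through.** **Starting point.** With two occasions, the arm-by-time test of the ANOVA equals a two-sample t-test on change. On the section 9.2 inputs (difference 1.6, SD 2.0, 17 per arm, two-sided 0.05) the standardised effect is 1.6/2.0 = 0.8, and noncentral-t power is 0.619, not the stated 80%. That gap is a separate matter. It is noted here only because the powers below start near 0.6.

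**1. Undefined values.** log10(0) does not exist. If a share p of an arm of 17 scores 0, the chance of at least one undefined value is 1 - (1 - p)^17:

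- p = 2%: 29%
- p = 5%: 58%
- p = 10%: 83%
- p = 20%: 98%

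These shares are assumptions; the protocol gives none. Transforming the change score instead does not help, because patients with no change or worse pain then have no defined log.

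**2. A different contrast.** A fall from 10 to 5 and a fall from 6 to 1 are both a change of 5 under section 9.1. On the log10 scale they are log10(10/5) = 0.30 and log10(6/1) = 0.78.

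**3. How often the rule meets a zero.** The protocol gives no NRS distribution, so I assumed:

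- integer scores limited to 0-10
- baseline mean 7.5 or 8, SD 1.5, limited to 5-10
- change SD 2.0 and 17 per arm
- mean change GNB/control of 2.5/0.9, 3.5/1.9, 4.3/2.7 or 5.0/3.4, each pair differing by 1.6

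That makes eight scenarios, simulated with 2,000 to 4,000 trials each. A post-treatment score of 0 occurs in 2-21% of GNB patients and 0.3-7% of controls. The protocol does not say which quantity Shapiro-Wilk is applied to, and this matters:

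| Normality tested on | Rejection together with at least one 0 |
|---|---|
| Residuals of change | about 5-16% of trials |
| Raw post-treatment scores | about 6-53% of trials |

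**4. Power.** With log10(x+1) used only when normality is rejected, and raw change otherwise, the loss against raw change is about 0.3-1.1 percentage points (change residuals tested) or about 1-4 points (raw post scores tested). If the log were applied in every trial, power would be 0.59-0.61 on raw change, 0.51-0.55 with log10(x+1), 0.56-0.58 with a rank-sum test of change, and 0.36-0.51 with log10 and zeros excluded. The every-trial figures rank the options; they are not the cost of the conditional rule.

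**5. Missing-data model read literally.** Randomisation makes the expected arm difference 0 at baseline, and the design assumes 1.6 afterwards. An arm effect without an interaction averages the two: (0 + 1.6)/2 = 0.8. Take equal SDs s at both occasions and pre/post correlation r (assumed). A change SD of 2.0 gives 2s²(1 - r) = 4, so the variance of a patient's pre/post mean is s²(1 + r)/2 = (1 + r)/(1 - r). The standardised effect is 0.8/√[(1 + r)/(1 - r)]:

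- r = 0.2: 0.65, power 0.455
- r = 0.5: 0.46, power 0.257
- r = 0.7: 0.34, power 0.158

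The change contrast has power 0.619. In simulation with one post score missing, a model with fixed arm, time and arm-by-time and a random patient effect recovers effects of 1.58-1.65 with power 0.60-0.63.

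**The case against.** **The power cost is small.** A reader might infer from the every-trial figures that the log rule costs five to nine points of power. It does not. The log applies only after rejection, and with an offset the loss is then about one point if change residuals are tested. This stands. It does not repair the rule, because the protocol names no offset and the undefined values remain.

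**The upper rates depend on assumptions.** The only mean changes in the protocol are 3.5 and 0.7, taken from a trial with a two-week assessment, and the scenarios go beyond them. Change residuals are also the natural quantity to test, which favours the 5-16% range. Pooling raw pre and post scores would give far higher rates, but that is the least defensible reading and I do not rely on it. The complete relief in section 2.3.2 is anecdotal. All of this bears on frequency, not on whether the rule works.

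**The protocol allows non-parametric tests.** It does so in general terms, when describing presentation, and it assigns Wilcoxon tests to the time endpoints and baseline variables. For the NRS, log10 is the only remedy named. An offset could sit in a statistical analysis plan, but the protocol has already fixed a plain log for this endpoint.

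**The ratio scale is a legitimate choice.** A pre-specified log analysis can be sound in itself. Here it conflicts with the hypothesis and effect size the protocol states.

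**The missing-data sentence need not exclude the interaction.** A reader might infer that the protocol prescribes a model targeting half the effect. The text does not establish that. The sentence classifies two factors, follows a two-factor ANOVA reported by arm and time point, and serves a null hypothesis about difference in change, so the interaction may have been meant to carry over. Full model terms are also commonly left to the analysis plan. What stands is that calling two designed occasions random, and naming arm as the only fixed factor, is wording that misleads.

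**Conclusion.** The log10 rule is wrong as written. It cannot be applied to a score of 0, it fails for the patients who did best, and where defined it tests something other than the difference in mean change. That conclusion needs no distributional assumption. Its frequency does: under the assumed scenarios, the rule meets at least one zero in about 5-16% of trials or about 6-53%, depending on what is tested for normality. The harm lies mainly in undefined values, or in excluding the best responders, rather than in power lost through an offset.

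The missing-data sentence is a secondary wording correction. The 0.8 target and the powers of 0.158 to 0.455 hold only on a literal reading. The protocol gives no missing rate for the post-treatment score taken in the ED, so how often this rule would apply is unknown.

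Both rules are conditional and the default ANOVA is sound in form. Severity is minor to should-fix.

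**What to change.** In section 9.4.1:

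1. Delete the log10 rule for the NRS, and exempt the NRS from the general log10 statement at the start of the section. Analyse it untransformed.
2. State that the primary test in the repeated-measures ANOVA is arm-by-time, that is, the difference between arms in mean change.
3. Add a rank-based or permutation test of change as a sensitivity analysis.
4. Reword the missing-data sentence: a mixed model with fixed arm, time and arm-by-time and a random patient effect, testing arm-by-time.

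The cost is a few reworded sentences. No new data are needed and the default ANOVA is unchanged.
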